## **B.8. EVALUATION CRITERIA**

### **B.8.1. EFFECTIVENESS**

Results of the tests and standard questionnaires will be recorded in Case Report Forms at Baseline and during follow-up visits. Changes from Baseline will be calculated.

Effectiveness will be measured for each subject using the following tests:

- Pain
- Visual Analog Scale (VAS, 10 cm) at Baseline, End of Trial Phase, Months 1, 3, 6 and12 monthsDisability
  - Pain Disability Questionnaire at 3, 6 and 12 months
- Impression of Change in Quality of Life
  - Patient Global Impression of Change at 3, 6 and 12 months
- Satisfaction with Therapy
  - Subject Satisfaction Questionnaire at 3, 6 and 12 months
- Paresthesia generated by the stimulation
  - Paresthesia Questionnaire at 3, 6 and 12 months

Study personnel will be appropriately trained for administration of each test.

### **B.8.3. SAFETY**

Safety will be assessed by characterizing study-related adverse events at all study visits with descriptive statistics.

#### **B.8.3.1 DEFINITIONS**

An adverse event (AE) is any untoward medical occurrence in a subject associated with the use of the therapy under the study whether or not related to the Intellis™ SCS system or the study procedures. An AE is also any event related to any underlying medical condition, present at baseline, which increases in severity or frequency by a clinically meaningful amount during the study as determined by the Investigator. Study-related is defined as relating to device, procedure or therapy.

For all study-related adverse events, the Investigator will provide an assessment of the adverse event, its seriousness, treatment/intervention provided, relationship to the device/procedure/therapy, and resolution.

As the effectiveness measure in this study is upper limb pain, upper limb pain do *not* need to be reported as an adverse event unless it meets the definition of a serious adverse event. Investigators may, however, report any other study pain-related adverse events during the study.

A **serious adverse event** (SAE) is an adverse event that

- Leads to death
- Leads to serious deterioration in the health of the subject, that either results in
  - a life-threatening illness or injury (life-threatening is defined as at risk of death at the time of the event), or
  - a permanent impairment of a body structure or a body function, or
  - in-patient hospitalization or prolongation of existing hospitalization (in-patient hospitalization is defined as a hospital admission for a period of greater than 24 hours), or
  - medical or surgical intervention to prevent life-threatening illness or injury or permanent impairment to a body structure or a body function,
- Leads to fetal distress, fetal death, or a congenital abnormality or birth defect

An **unanticipated adverse device event** (UADE) is a serious adverse event that was not previously identified in nature, severity, or degree of incidence in the Clinical Study Plan, or any unanticipated serious problem associated with a device that related to the rights, safety, or welfare of subjects.

Known adverse events related to the device, procedure or therapy are listed in the section C. (Risk Analysis) of this Clinical Study Plan.

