### **B.8.3.2 REPORTING**

Reported AEs, SAEs and UADEs will be assessed and captured from enrollment through the completion of the study on the Adverse Event Source Worksheet. Study-related is defined as relating to the device, procedure or therapy. The assessment/evaluation can be performed initially by a designee, but the Investigator will make the final determination.

Only adverse events that are evaluated by the Investigator to be study-related will be captured on the CRF.

All study-related adverse events will document seriousness, severity, treatment/intervention provided, relationship to the device/procedure/therapy, and resolution.

AEs and SAEs will be reported as required by the IRB.

As would be the common practice when using commercial medical devices, device - related AEs may be reported by the site (per their institutional policy) to the Customer Service or Technical Support of Medtronic as specified in the manufacturer's labeling/manuals.

Data Monitoring Committee will not be used as this is a post-market open label study and will adhere to all IRB reporting requirements and the device manufacturer's reporting requirements.

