***Study Risk Control Measures***

The following will be done to mitigate risks associated with the implanted system:

- Investigators who are experienced with spinal cord stimulation implantation techniques will be utilized
- Instructions will be given to the study participants to ensure they can properly use the patient programmer and recharger system
- Subjects can turn off stimulation at any time during the study with the patient programmer or recharger
- Periodic monitoring of the study participants
- Written materials that contain precautions, warnings, and contraindications, as well as instructions on the use of the devices will be available and/or provided to the clinicians and subjects

Since the efficacy measure in this study is intensity of pain in the upper limbs, pain in these areas does not need to be reported as an adverse event unless it meets the definition of a serious adverse event. However, Investigators may, at their discretion, report any other pain-related adverse events during the study.

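### The exemption of non-serious upper limb pain from AE reporting makes no exception for study-related pain, so the AE-frequency endpoint can under-count it

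*Combined protocol and SAP*

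**What the plan says.** B.8.3.1 gives a general AE definition and then an exception to it. The definition includes any underlying condition "present at baseline, which increases in severity or frequency by a clinically meaningful amount during the study as determined by the Investigator". The exception opens with its reason, "As the effectiveness measure in this study is upper limb pain", and concludes that "upper limb pain do *not* need to be reported as an adverse event unless it meets the definition of a serious adverse event". The next sentence leaves discretion for other pain only: "Investigators may, however, report any other study pain-related adverse events during the study".

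C.1, under Study Risk Control Measures, repeats the exemption, again for upper limb pain, in similar words: "pain in these areas does not need to be reported as an adverse event unless it meets the definition of a serious adverse event".

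B.8.3.1 also fixes what counts as related: "Study-related is defined as relating to device, procedure or therapy". B.8.3.2 then restricts what reaches the database: "Only adverse events that are evaluated by the Investigator to be study-related will be captured on the CRF". B.8.3 plans a descriptive account of study-related AEs at all visits, and B.7.4 makes the frequency of treatment emergent AEs a secondary endpoint.

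**The concern.** Exempting the pain under treatment from AE reporting is understandable: its ordinary ups and downs are an efficacy matter and would clutter the safety listing. The difficulty is that the exemption is worded by body region and seriousness alone. It says nothing about cause, about whether the pain is new, or about whether it is worse than at Baseline. A subject with new arm pain after lead placement, or with arm pain above the Baseline level that the Investigator attributes to stimulation, meets the plan's own definition of a study-related AE. Yet no report is required unless the event is serious.

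At stake is the AE-frequency endpoint in a study that has collecting safety data among its stated objectives. If reporting of this event is left to each site's habit, the published frequency mixes true occurrence with willingness to report, and the error can only run downward.

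**Working it through.** The plan states no figure on this point, so the main check is a comparison of passages.

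1. **Definition against exemption.** Under the B.8.3.1 definition, clinically meaningful worsening of a baseline condition is an AE. Upper limb pain is the baseline condition of every subject. The exemption in the same section, and again in C.1, lifts the reporting duty for that condition unless the event is serious. Neither place excepts pain related to device, procedure or therapy. The discretionary sentence concerns other pain, so it does not restore the duty. A.2 admits subjects with unilateral pain, and the wording does not separate the limb affected at Baseline from new pain in the other arm.

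2. **What the exemption can change in the endpoint.** Take non-serious upper limb pain and split it by the Investigator's judgment:

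| Investigator's judgment | On the CRF without the exemption? | On the CRF with the exemption? |
|---|---|---|
| Not study-related | No (B.8.3.2) | No |
| Study-related | Yes | Only if the site chooses to report it |

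The first row is the same either way. The only row that can change is the second, and it can only fall. Serious cases stay reportable throughout.

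3. **Whether the VAS fills the gap.** Table 1 schedules the VAS at enrollment, at end of trial and at 1, 3, 6 and 12 months. None is scheduled at implant or activation. The longest interval that the windows allow between the end-of-trial VAS and the 1-month VAS is 60 days (trial end to implant) + 14 days (implant to activation) + 45 days (30 + 15, taking a month as 30 days) = 119 days, and it contains the implant procedure. Under B.6.6, subjects who fail the trial and are not implanted are followed for two weeks after lead removal for AEs, with no VAS scheduled. B.5.4.1 expects about 55 trialed and about 45 implanted, which leaves about 55 − 45 = 10 subjects who are not implanted. Where a VAS is taken, it gives intensity but no cause, treatment or resolution.

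4. **Scale.** One uncounted subject is 1/45 = 2.2 percentage points of the implanted group or 1/55 = 1.8 points of the trialed group. The documents give no rate for related, non-serious upper limb pain. With assumed rates p, the expected number of subjects with such an event is n × p, and the chance of at least one is 1 − (1 − p)^n:

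| Assumed p | n = 45: expected | n = 45: chance of ≥ 1 | n = 55: expected | n = 55: chance of ≥ 1 |
|---|---|---|---|---|
| 2% | 0.9 | 59.7% | 1.1 | 67.1% |
| 5% | 2.25 | 90.1% | 2.75 | 94.0% |
| 10% | 4.5 | 99.1% | 5.5 | 99.7% |

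These are occurrences under an assumption, not counts of missing reports. Some would be reported voluntarily or under another term.

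5. **Reading a zero.** With complete reporting, no cases in 45 subjects would give a one-sided 95% upper limit of 1 − 0.05^(1/45) = 6.4%. That limit does not apply to an event that need not be reported.

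**The case against.** The strongest reply is that this is a general rule followed by a specific exception with a stated reason, which is a legitimate design choice in a post-market, single-arm, descriptive study with no hypothesis. The primary endpoint is untouched and no decision depends on the AE frequency. Other capture also exists. The likely causes of device-related arm pain, such as lead migration, infection, hematoma or changed stimulation, remain reportable in their own right. Unscheduled visits can occur at any time (B.6.9). Medication use is recorded at every visit (Table 1). B.9.2 reports ranges, so a worst change at 3 months that is a worsening would show. A study-related AE leading to withdrawal is followed up (B.6.17).

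Much of this stands, and it limits the importance of the point. It does not remove it: none of these routes attributes a cause to arm pain that has no other reportable diagnosis.

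Four stronger readings are tempting, and the documents do not support them:

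- A reader might infer that upper limb pain is the harm most specific to a cervical implant. The harms that C2 and D.1.2.1 tie to a higher insertion level are direct cord trauma, hemorrhage, hematoma and paralysis, and all remain reportable.
- A reader might infer that the endpoint does omit these events and is therefore known to be biased low. The wording makes reporting unnecessary, not forbidden, so the endpoint can omit them.
- A reader might infer that the exemption serves only to hide related harm. That its effect is confined to related events is true of the CRF. On the source worksheet, where B.8.3.2 has reported AEs captured before the CRF filter, it also spares sites from logging unrelated fluctuation, which fits its stated reason.
- A reader might turn an assumed rate into a number of missing subjects. That would further assume no voluntary reporting and no capture under a causal term.

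**Conclusion.** The point holds as a gap in the reporting rule. The exemption for non-serious upper limb pain has no exception for pain judged study-related, and it is at odds with the AE definition beside it and with the aim of characterizing study-related AEs. For the AE-frequency endpoint its only possible effect is under-counting of related, non-serious upper limb pain. How much is unknown: it depends on an event rate that the documents do not give and on how often sites report voluntarily. The conclusion rests on reading the exemption as written, without an unstated exception by cause, and on the CRF being the source of the endpoint. The change is a cheap improvement; the primary endpoint is not affected.

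**What to change.** In B.8.3.1 and, in matching words, in C.1:

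- Limit the exemption to pre-existing upper limb pain that is not worse than Baseline or is not judged study-related.
- Require AE reporting of upper limb pain that is new in site or character, or worse than Baseline, when the Investigator judges it related to device, procedure or therapy.

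B.8.3.2 can stand, since its CRF rule then works as intended.

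Optionally, tabulate at each visit the number of subjects whose upper limb VAS exceeds Baseline. This uses data already collected and gives a count that does not depend on attribution.

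The cost is two wording changes, a few more AE forms and a slightly higher reported AE frequency. If some subjects were already followed under the old rule, the report should say from which date the new one applied.

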### **B.8.3.2 REPORTING**

Reported AEs, SAEs and UADEs will be assessed and captured from enrollment through the completion of the study on the Adverse Event Source Worksheet. Study-related is defined as relating to the device, procedure or therapy. The assessment/evaluation can be performed initially by a designee, but the Investigator will make the final determination.

Only adverse events that are evaluated by the Investigator to be study-related will be captured on the CRF.

All study-related adverse events will document seriousness, severity, treatment/intervention provided, relationship to the device/procedure/therapy, and resolution.

AEs and SAEs will be reported as required by the IRB.

As would be the common practice when using commercial medical devices, device - related AEs may be reported by the site (per their institutional policy) to the Customer Service or Technical Support of Medtronic as specified in the manufacturer's labeling/manuals.

Data Monitoring Committee will not be used as this is a post-market open label study and will adhere to all IRB reporting requirements and the device manufacturer's reporting requirements.

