#### **A.4. DURATION OF THE INVESTIGATION**

The expected total duration of this study is approximately 26 months. Enrollment of subjects is expected to last 20 months. Subjects that have received the permanent implant will be followed up for 12 months after their device has been activated. A subject will likely be committed to the study for about 14 months. This consists of Baseline assessments, up to 10 days of trial stimulation, and 12 months of treatment following implantation and activation of the device. All current subjects or those who have completed their 6-month visit will be offered to return for an additional 12-month visit. This would increase their commitment to the study to 14 months.

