### **B.6.12. 3 MONTHS AFTER DEVICE ACTIVATION ( $\pm$ 21 DAYS)**

Subjects will visit the study site where they will be assessed for pain, other pain (if applicable), extent of disability, Patient Global Impression of Change, and subject satisfaction. Paresthesia generated by the stimulator will be assessed. Programming adjustments may be made, as needed. Anterior-posterior (AP) and lateral X-ray imaging will be done. Subjects will also be assessed for possible study-related adverse events and medication usage. If there are no ongoing study-related adverse events, the subject will complete the study at this visit. In situations where there is an ongoing study-related adverse event, subjects will be followed until resolution of that adverse event or determination that the subject's condition is stable, at which point the Study Completion CRF should be completed.

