### **B.6.19. STUDY SUSPENSION AND TERMINATION**

Subjects will be considered to have completed all study requirements following the completion of the follow up visit 3 Months after Device Activation. All subjects who remain implanted at the time of Study Completion will be offered to return for an additional visit 6-months after device activation.

Each clinical site will be considered to have completed study requirements at the end of the required monitored close out visit. The study will be considered terminated when all of the requirements of this Clinical Study Plan have been fulfilled, all close out visits have been completed and all Sponsor and Investigator reports have been issued and reported to the IRB.

The Sponsor, the Investigators, or the IRB(s) may suspend or terminate the study early at any time. If the study is suspended or terminated prematurely, all subjects that are still enrolled will be terminated from the study. A Study Completion CRF will be completed noting that the study has been terminated. If there is an ongoing study-related adverse event, the subject will be followed until resolution of the adverse event or determination that the adverse event is not likely to change.

Subsequent follow-up of the subjects after study completion will be the responsibility of the subject's personal physician.

The Sponsor reserves the right to terminate the study but intends only to exercise this right for reasons related to the protection of subjects or valid scientific or business reasons. The Sponsor will notify Investigators and IRBs in writing in the event of study termination.

The Sponsor reserves the right to stop the enrollment of subjects at any clinical site at any time after the clinical site initiation. Possible reasons for suspending or terminating a clinical site may include, but are not limited to

- Non-compliance by Investigator
- Failure to obtain proper written informed consent
- Repeated failure to complete or submit CRFs in a timely manner
- Failure to report study-related serious adverse events (SAEs) or unanticipated adverse device events (UADEs) to the Sponsor within 48 hours of knowledge of the event and to reviewing IRB in accordance with its policies

- Repeated failure to comply with clearance of queries generated during monitoring of the study
- Inactivity

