### **B.7.4. SECONDARY ENDPOINTS**

The following secondary endpoints will be evaluated:

- Change from Baseline in upper limb pain mean VAS score determined at the 3-month visit after device activation. This is calculated as: Change from Baseline in Upper Extremities Pain VAS = 3-Month Visit Pain VAS – Baseline Pain VAS. A negative result reflects a decrease in Pain VAS score, while a positive result reflects an increase in Pain VAS score.
- Change from Baseline in extend of disability as measured by mean Pain Disability Index (PDI), evaluated at 3 months after device activation.
- Frequency of treatment emergent adverse events.

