**Table 1. Schedule of Study Activities**

Activity	Pre-Trial Phase		Trial Phase		Permanent Phase					12 months visit (±31 days after activation)
	Enrollment	Baseline	Start Trial Phase	End Trial Phase (up to 10 days after trial starts)	Permanent Implant (up to 60 days after end of trial)	Device Activation (0-14 days after implant)	1-month visit (±15 days after activation)	3 months visit (±21 days after activation)	6 months visit (±31 days after activation)	
Informed Consent	X									X b)
Pain Intensity Evaluation (VAS)	X			X			X	X	X	X
Medication Use	X	X	X	X	X	X	X	X	X	X
Medical/Surgical History	X	X								
Eligibility Criteria Evaluation	X									
Pain Disability Questionnaire		X							X	X
AP/Lateral x-ray imaging			X	[X]	X	[X]	[X]	X	[X]	[X]
Paresthesia Questionnaire								X	X	X
Patient Global Impression of Change								X	X	X
Subject Satisfaction								X	X	X
Adverse Event Monitoring		X	X	X	X	X	X	X	X	X
Device Programming			X			X	[X]	[X]	[X]	[X]
Device Programming Log				[X]			[X]	[X]	[X]	[X]
Study Completion				X a)				[X] c	[X] c	X c

[X] Optional activity.

a) For subjects that do not have a successful Trial Phase.

b) Some subjects may need to be reconsented to complete these visits.

c) Some subjects were originally consented to complete the study at the 3 or 6 month visit and may not consent for additional visit.

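### Adverse event frequency has no time window, denominator or exposure although follow-up is 3, 6 or 12 months, and new events between a subject's completion and later return may be missed

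*Combined protocol and SAP*

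**What the plan says.** **Capture window.** B.8.3.2 states that AEs "will be assessed and captured from enrollment through the completion of the study". It does not say whether completion is the subject's or the study's.

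**When a subject completes.** The current text gives several answers.
- B.6.12 (3-month visit): "If there are no ongoing study-related adverse events, the subject will complete the study at this visit".
- B.6.19: "Subjects will be considered to have completed all study requirements following the completion of the follow up visit 3 Months after Device Activation"; those still implanted "will be offered to return for an additional visit 6-months after device activation".
- B.6.18 expects everyone to attend through 12 months, yet in the next sentence offers 12 months as an extra visit. B.6.14 calls that visit optional.

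**Who may return.** A.4: "All current subjects or those who have completed their 6-month visit will be offered to return for an additional 12-month visit". B.6.13 and B.6.18 extend the 12-month offer to everyone still implanted at completion. Table 1, footnote b, says some may need new consent. Footnote c adds: "Some subjects were originally consented to complete the study at the 3 or 6 month visit and may not consent for additional visit".

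**After completion.** B.6.12 and B.6.18 follow only study-related AEs that are already ongoing. B.6.19 passes later follow-up to the personal physician. B.6.14 has AEs assessed at 12 months, with no look-back period.

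**Analysis.** The safety endpoint in B.7.4 reads in full: "Frequency of treatment emergent adverse events". The other two endpoints in that list are tied to 3 months. B.8.3 promises descriptive statistics at all visits, and B.9.2 promises frequency distributions. B.7.1 defines one population (implanted, completed, no major deviations) and does not say whether it applies to safety.

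**The concern.** Two separate problems arise.

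The first is capture. If completion in B.8.3.2 means the subject's own completion, a new event after the Study Completion form and before a return visit has no stated route into the database. One site could record it and another could leave it out, and both would be following the plan.

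The second is summary. Subjects will be observed for 3, 6 or 12 months, in shares set by which version of the consent they signed and whether they agreed to more. The revision history (April 2020; February 2021, 6-month visit added; July 2021, 12-month visit added) makes such a mix plausible. A proportion over all implanted subjects would then change with the mix even if the device's risk did not.

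Collecting safety data is a secondary objective, there is no data monitoring committee, and about 45 implants are planned, so a few events matter. The risk section itself describes tissue growth around the lead with onset from weeks to many years, and possible revision for infection, malfunction or migration. These later events are the most exposed to both problems. The 3-month primary endpoint is not affected.

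**Working it through.** The plan states no AE rate, precision target or cohort shares, so there is no figure to reproduce. What follows is illustration under stated assumptions.

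**Inputs.** From the documents: about 45 implanted subjects (B.5.4.1); stopping at 3, 6 or 12 months (Table 1, footnote c). Assumed: a 12-month risk I of 5% to 30%; four mixes of stopping times; complete observation up to each stop; time counted from activation.

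**1. Pooled frequency, constant hazard.** Risk by month t is 1 − (1 − I)^(t/12). For I = 20%:
- 3 months: 1 − 0.80^0.25 = 5.43%
- 6 months: 1 − 0.80^0.5 = 10.56%
- 12 months: 20%

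With one third stopping at each time: (5.43 + 10.56 + 20)/3 = 12.0%. In 45 subjects that is 5.4 with an event, against 9.0 under full follow-up.

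**2. Varying the mix and the event pattern.** The front-loaded case assumes 70% of 12-month events by month 3 and 85% by month 6. Its ratio is 0.70a + 0.85b + c for shares a, b, c stopping at 3, 6 and 12 months.

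| Share stopping at 3/6/12 months | Pooled ÷ 12-month risk, constant hazard (I = 5-30%) | Same, front-loaded |
|---|---|---|
| 10/10/80% | 0.88 | 0.955 |
| 20/20/60% | 0.75-0.77 | 0.91 |
| one third each | 0.59-0.61 | 0.85 |
| 50/25/25% | 0.50-0.53 | 0.81 |

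**3. Person-time.** For I = 20%, the hazard is −ln(0.80)/12 = 0.0186 per month. With one third stopping at each time, mean time at risk is 0.1199/0.0186 = 6.45 months. Events over person-time return 0.0186 per month, and 1 − exp(−12 × 0.0186) = 20%. The mixing disappears if the hazard is constant. If events are front-loaded, one overall rate is not enough and results by period are needed.

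**4. Gap loss, a separate effect not included above.** Suppose a returner's gap events are never recorded. The share of first events that fall in the gap, under constant hazard, is:
- 6 to 12 months: (0.8944 − 0.80)/0.20 = 47% for I = 20%; 49% for I = 10%
- 3 to 12 months: (0.9457 − 0.80)/0.20 = 73%; 74% for I = 10%
- 3 to 6 months, as a share of 6-month first events, I = 20%: (0.9457 − 0.8944)/0.1056 = 49%

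If the return visit records gap events, the loss is zero.

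**5. Duration check.** A.4 gives 20 months of enrollment and about 14 months' commitment, so 34 months in all, against 26 stated. If the study closed at 26 months with uniform enrollment, (26 − 14)/20 = 60% of subjects could reach 12 months. Unequal follow-up could therefore arise without any refusals.

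**The case against.** A reader might infer four stronger things that the documents do not support.

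- **That the plan pools everyone into one crude figure.** It does not say so. B.8.3 speaks of all study visits, which leaves room for reporting by visit. The defect is that no method is fixed, so pooling is permitted.
- **That gap events are excluded and later harms are lost.** Completion in B.8.3.2 may mean the close of the study, which B.6.19 defines separately; gap events would then be inside the window. The 12-month visit checks AEs and medication, with imaging optional, and a revised system or persistent pocket pain could surface there. Against this, the plan uses completion for individual subjects and has a special rule for AEs ongoing at that point, a rule hardly needed if capture continued for everyone. The subject-level reading is the more natural one, but it is not certain.
- **That three quarters of follow-up is routinely unobserved.** A direct return from 3 to 12 months rests only on the general wording in B.6.13 and B.6.18. The explicit 12-month offer names current subjects and those who finished 6 months. Subjects who simply continue have no gap. The timing of new consent is not stated, and E.4 allows it by mail and telephone.
- **That the frequency is understated by a known amount.** Mix and hazard are assumed. Trial and surgical events before activation are captured for everyone from enrollment, which pushes the pattern towards front-loading and a smaller bias.

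It also stands that the study is descriptive and tests no hypothesis. A descriptive frequency still needs a period and a denominator to be readable.

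**Conclusion.** The concern holds as a gap in specification with a foreseeable direction. Follow-up is unequal by design. No passage settles how a new event between completion and return is captured, and the safety endpoint has no time window, denominator or exposure. Followed as written, the plan permits a frequency that is neither a 3-month nor a 12-month risk, and later device events may be understated.

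The size cannot be determined from the documents. Before any gap loss, a pooled figure read as 12-month risk would show about 50-88% of it under constant hazard and about 81-96% with front-loaded events, for the mixes in the table. Gap loss could add to this or be zero. The point should be acted on, because a better method is specific and cheap.

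**What to change.** 1. **B.6.13, B.6.14 and B.8.3.2.** Define the AE window for each subject. For anyone who returns after a Study Completion form, collect study-related events, revisions, explants and related procedures since that form's date. Use both the subject and the medical record, take onset dates, and flag the entries as retrospective.
2. **B.7.4 and B.9.2.** Report AEs by period: trial phase for all trialed subjects; then implant to 3 months, >3-6 and >6-12 months for implanted subjects. Give the number at risk in each, plus events per device-month observed. Make the period through the 3-month visit the main common window. Do not restrict the endpoint to implanted subjects from implant onward: that would drop trial-phase events and the roughly 10 subjects trialed but not implanted (about 55 less about 45, B.5.4.1).
3. **B.6.12, B.6.13, B.6.18 and B.6.19.** Reconcile the statements on when a subject completes, and check the 26-month duration in A.4 at the same time.

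The cost is one set of look-back questions and a records check at a visit that already exists, and a revised safety table. The downside is some recall error in the retrospective part, which the flag makes visible.
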